#### Overview

Potential participants will complete a telephone and an in-clinic screening to determine eligibility for this study. Eligible participants will be randomized to receive one of two treatment conditions: 1) Zonisamide plus *Take Control* (a computerized alcohol reduction and medication compliance program developed by the National Institute on Alcohol Abuse and Alcoholism (NIAAA)); 2) a placebo plus *Take Control*. For both conditions, participants will receive 12 treatment sessions. Participants will receive medication at each session, and they should have two weeks worth of medication on hand at any given time. Participants will take the medication as prescribed at home. The first 11 treatment sessions will include *Take Control*. The 12 treatment sessions will be followed by two drug dose taper sessions, and a follow up phone interview immediately following the final session.

Participants will also undergo two scans of less than 2 hours duration, one before they begin study sessions and the second near the end of the study (12th study week and before the medication taper). At the in-clinic screening session, participants will receive a “MRI Information for Research Participants” handout that answers some commonly asked questions about MRI and tells participants what they can expect while undergoing an MRI scan. Both scans will be conducted at BU CILSE. Participants will be screened before each scan session for pregnancy (urine sample, women of childbearing potential only), recent smoking or alcohol use (breathalyzers), and illicit substance use (urine sample). Participants will be asked to complete the Alcohol Urge Questionnaire (AUQ) before and after the scan. Participants will also be asked to complete item #8 from the AUQ before and after the Alcohol Cues Task. Eligible participants will complete a 1-hour 3 Tesla MRI scan involving structural imaging (MRI) and functional imaging (fMRI). The fMRI scans include a resting-state scan (no task involved) a cognitive (Stroop) task, and an alcohol cue reactivity task. The latter two scans involve presentation of visual images to participants while they are in the scanner. No contrast agent or invasive procedures are used. Only personnel trained in working in high magnetic field environments will work on this project. Imaging data will be analyzed on secure networks using only encrypted files. All data obtained will be coded to protect participant privacy and confidentiality.

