#### V. Neuropsychological Assessments

Neuropsychological function will be assessed using Hopkins Verbal Learning Test (HVLT), Wechsler Adult Intelligence Scale-IV's (WAIS-IV) Letter-Number Sequencing and Digit Span, WMS-IV Symbol Span, Delis-Kaplan Executive Function System (D-

KEFS) Letter Fluency and the Wide Range Achievement Test-IV (WRAT-IV). Impulsivity will be evaluated using the CPT and the Go/No Go task. Risk taking behaviors will be measured with the Balloon Analog Risk Task and the Rogers Risk task during weeks 1 and 12. Functional and structural images will be acquired during the Stroop test and Alcohol Cues task during fMRI imaging sessions, which will be administered at study weeks 1 and 12.

- A. Hopkins Verbal Learning Test-Revised (HVLT-R; Brandt & Benedict, 2001)** – The HVLT-R is a brief assessment of verbal learning and memory (recognition and recall) for individuals 16 years and older. The HVLT-R requires recall of a series of 12 words over three learning trials, free recall after a delay, and a recognition trial. The assessment takes approximately 5-10 minutes, with a 25-minute delay, to complete.
- B. Wide Range Achievement Test-IV (WRAT-IV; Wilkinson, G. S., & Robertson, G. J., 2006)** – The WRAT-IV is a norm-referenced test that measures the basic academic skills of word reading, sentence comprehension, spelling, and math computation.
- C. Symbol Span: Wechsler Memory Scale (WMS-IV; Wechsler, 2009)** – The WMS-IV is a neuropsychological test designed to measure the various memory functions of a person. The measure includes 7 subsets and A person's performance is reported as five Index Scores: Auditory Memory, Visual Memory, Visual Working Memory, Immediate Memory, and Delayed Memory.
- D. Delis-Kaplan Executive Function System-Letter Fluency (D-KEFS; Delis, Kaplan, & Kramer, 2001)** – D-KEFS is a neuropsychological test used to measure a variety of verbal and nonverbal executive functions (reasoning, planning, problem solving, etc.) for both children and adults (ages 8-89 years).
- E. Digit Span and Letter Number Sequencing: Wechsler Adult Intelligence Scale (WAIS-IV; Weschler, 2008)** - The WAIS-IV is a neurological test developed to assess cognitive ability in adults. This instruments aids in examining the relationship between intellectual function and memory. The test includes 11 subtests of various formats. Approximately 60 to 90 minutes is required for completion.

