Subjects in all groups will be asked to view *Take Control* (TC)—a novel computerized alcohol reduction and medication compliance program derived from the National Institute on Alcohol Abuse and Alcoholism's (NIAAA's) self-help approach, *Rethinking Drinking*. *Take Control* consists of 11 motivational and educational modules, which will take around 1.5 hours in total.

All subjects will receive standard medication management during each visit, with additional adherence counseling, when needed.

*Assessments:*

I. Medical Assessments:

- a. Vital signs (i.e. body temperature, pulse rate, respiration rate, and blood pressure)
- b. Weight
- c. Urine Drug Screen (A general toxicology screen will be done to identify substances that may be affecting the patient and to ensure subject safety. A list of drugs and/or metabolites analyzed and their corresponding limits of detection is provided in the appendix attached).
- d. Urine HCG test (for women of child-bearing potential only)
- e. Alcohol Breathalyzer
- f. Clinical Laboratory assessments (from blood sample by venipuncture):
  1. Comprehensive Metabolic Panel
  2. Bicarbonate
  3. Liver Function Tests (LFTs)
  4. Gamma-glutamyl transpeptidase (GGT)
  5. Complete Blood Count with Differential (CBC with diff)
- g. Birth Control Assessment (for women of child-bearing potential only)

II. Clinical Administered Assessments/Self-Report Measures:

Clinician administered assessments and self-report measures will be completed at various treatment sessions. See Table 1 for detailed information on the timing and assessment schedule.

Post-Treatment Period

Follow-up assessments will be obtained at the end of the final week of drug treatment, i.e. study week 14, and a phone interview at study week 16. During the follow-up interview, the subject will provide data for the TLFB and for reports on adverse events (AEs), and concomitant medications.

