#### Data Analysis

1. Demonstrate that ZON will attenuate changes resulting from performance on alcohol-word and negative-word Stroop tasks in the activity of frontal-parietal and midbrain regions and the connectivity to networks associated with these regions in AUD subjects. Our working hypothesis is that midbrain activity will be lower in ZON treated subjects than in placebo subjects following performance on alcohol and negative emotion Stroop task, which will occur in association with enhanced mid-brain-frontal connectivity and increased synchrony.

Fixed effects models will be used to analyze data for brain activation in regions of interest, with treatment group as a between group factor and Stroop task type and order of stimuli presentation will be within subject factors. Regions of interest will include parahippocampal gyri, midbrain substantia nigra and red nucleus, dorso-lateral prefrontal cortex, and cerebellum.

Connectivity will be assessed using the Free Surfer analysis described below. Seeds will be used for the dorsolateral prefrontal cortex and the midbrain (substantia nigra) following Muller-Oehring et al. (2013).

2. Demonstrate that ZON administration attenuates the enhanced regional brain activity and craving- induced by exposure to alcohol related cues in AUD subjects. Our hypothesis is that exposure to alcohol-related cues will increase brain activity in select limbic and prefrontal areas to a lesser degree in ZON as compared to placebo treated AUD subjects.

Fixed effects models will be used to analyze data for brain activation in regions of interest, with treatment group as a between group factor and stimulus type and order of stimuli presentation was within subject factors. Regions of interest, based on the meta-analysis of Schacht et al. (2013), will include the ventral striatum, medial prefrontal cortex, and the anterior cingulate cortex.

3. Demonstrate that the ZON induced changes in brain activity are predictive of reduced ethanol consumption.

Logistic regression analysis will be used to evaluate zonisamide-induced decreases in the BOLD response in the ventral striatum and the medial prefrontal cortex as predictors of complete abstinence or reduction to safe drinking levels (defined as consumption of no more than more than 2 standard drinks per day) during study weeks 10 to 12.

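### Aim 3 promises that BOLD decreases predict reduced drinking, but the change score is not complete until the week-12 scan, after 67% to 95% of the outcome days, so it supports only a concurrent association

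*Combined protocol and SAP*

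**What the plan says.** Section L, Data Analysis, item 3 states the aim: "Demonstrate that the ZON induced changes in brain activity are predictive of reduced ethanol consumption". The method is: "Logistic regression analysis will be used to evaluate zonisamide-induced decreases in the BOLD response in the ventral striatum and the medial prefrontal cortex", entered as predictors of a binary drinking outcome. That outcome is complete abstinence or consumption at or below two standard drinks a day, assessed "during study weeks 10 to 12".

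Section L, Overview, plans two scans, "one before they begin study sessions and the second near the end of the study", and places the second in the 12th "study week and before the medication taper". Section L, V. Neuropsychological Assessments, agrees on the week: the Stroop and cue tasks are run "during fMRI imaging sessions, which will be administered at study weeks 1 and 12".

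Drinking is also recorded after the second scan. The Post-Treatment Period text in Section L provides for "a phone interview at study week 16", at which Timeline Follow-Back (TLFB) data are taken, and Table 1 lists further TLFB collection after week 12. Item 3 uses none of this. It specifies no lag, no intermediate scan and no adjustment for earlier drinking, and nothing limits the aim to association.

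**The concern.** A decrease in BOLD response needs both scans, so the predictor does not exist until the week-12 scan is done. By then most of the drinking it is meant to predict has already happened.

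Participants who drank less in weeks 10 and 11 may show a weaker cue response in week 12 because they drank less. Brain change may equally have come first, or both may follow from something else, such as motivation or adherence. The model returns a coefficient in each case and cannot tell the cases apart. Followed as written, the plan would report a significant coefficient as prediction, which the design does not show.

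**Working it through.** **The plan's own figures.** No power or sample size is stated for the Aim 3 regression. The figures in the Power Analysis paragraph concern other comparisons. They reproduce with the two-sided normal approximation, power = Φ(d·√(n/2) − 1.96), at n = 40 per group:

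- Drinks per day, d = 0.74: 0.74 × √20 = 3.309; 3.309 − 1.960 = 1.349; power 0.911, against 0.9 stated.
- Ventral striatum group contrast, d = 0.70: 0.70 × √20 = 3.130; 3.130 − 1.960 = 1.170; power 0.879, against 0.88 stated.
- Dropout: 40 / (1 − 0.20) = 50 per arm, as stated.

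None of these depends on the timing question.

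**Inputs for the timing check.** The outcome window is weeks 10 to 12 (Data Analysis, item 3). The second scan is in week 12 (Overview; V. Neuropsychological Assessments). I assume nominal 7-day weeks with day 1 as the first day of week 1.

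**Day count.** Week w starts on day 7(w − 1) + 1. Week 10 starts on day 64, and week 12 runs from day 78 to day 84. The window is days 64 to 84, or 21 days. For a scan on day s, the share of the window already past is (s − 64)/21, not counting the scan day.

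| Scan day | Outcome days before scan | Share |
|---|---|---|
| 78 (first day of week 12) | 14 | 67% |
| 81 (mid-week) | 17 | 81% |
| 84 (last day) | 20 | 95% |

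At most 7 of 21 days (33%), counting the scan day, fall on or after the scan.

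**Alternative reading of the window.** Suppose weeks 10 to 12 means TLFB collected at visits 10, 11 and 12 (days 64, 71 and 78), each covering the previous 7 days. The window is then days 57 to 77, and 21 of 21 days (100%) precede any scan on or after day 78. The protocol does not say which reading applies.

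**Where in week 12 the scan can fall.** The Overview requires the scan before the taper, but three places differ on when the taper starts. The Zonisamide text under Study Sessions starts it at week 12. The regimen table beneath that text lists weeks 7 to 12 as maintenance. The title of Table 1 puts the taper in weeks 13 and 14. On the first of these, the scan must fall at the very start of week 12 (67%). On the other two, it can fall on any day of that week (67% to 95%).

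**The case against.** The strongest reply is that time of measurement is not time of occurrence. The Zonisamide text and table bring participants to the target dose at about week 7 and expect steady state about two weeks after a dose is reached. A drug-related BOLD change could therefore exist before week 10 and merely be recorded in week 12. The window also matches the last three weeks of treatment used in the Power Analysis paragraph, so it is coherent for an on-drug mechanistic analysis. This stands as a reason to keep the window. It does not rescue the word predictive. The change in drinking may also have begun before week 10, and with no scan between baseline and week 12 the data cannot show which came first.

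A second reply is that predictor is ordinary regression vocabulary. That is fair for the method sentence, but the aim itself promises to demonstrate prediction.

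Three stronger readings are tempting, and the documents do not support them:

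- **That the whole outcome window precedes the scan.** By calendar days, even a last-day scan leaves 20 of 21 days before it. The 100% figure needs the visit-based reading, which is not stated.
- **That Section N (Benefits) rests its responder-selection claim on this regression.** Section N speaks in general terms of cue-task reactivity and mechanisms. It does not name Aim 3 or the change score, and it may mean reactivity at baseline, which does precede treatment.
- **That modelling drinking after the scan would deliver the promised test.** That period covers the taper and time off drug, so it asks a different question. With a target of about 80 participants in week 12 (2 × 40) and no power stated for Aim 3, a null result would say little.

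**Conclusion.** The concern holds in a limited form. At least 14 of the 21 outcome days (67%) precede the scan that completes the predictor. The range is 67% to 95% by calendar days, and 100% only under the visit-based reading. These shares assume nominal 7-day weeks and a second scan held in week 12 as planned.

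Aim 3 can support a concurrent association between BOLD change and drinking in weeks 10 to 12. It cannot support prediction, direction of effect or selection of likely responders. The problem is confined to this mechanistic aim. The randomised comparison of drinking in item 4, the safety analysis and the sample size are unaffected.

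**What to change.** 1. **Restate Aim 3 and its conclusion.** For example: to estimate the concurrent association between the change in BOLD response from baseline to week 12 and abstinence or safe drinking over weeks 10 to 12. State that the analysis does not establish which change came first, and do not cite it in support of prediction or responder selection. This costs only wording, and the price is a weaker claim.
2. **Define the window.** Say whether weeks 10 to 12 are calendar weeks or the periods covered by TLFB at visits 10 to 12, and record the scan date so that the share of the window before the scan can be reported.
3. **Optional exploratory model.** Relate BOLD change to TLFB drinking after the scan, through week 16, using data already planned. Label it as covering taper and off-drug time and as answering a different question. Show results with and without adjustment for drinking in weeks 10 to 12: without it, earlier drinking is left uncontrolled; with it, the effect of interest may be removed if BOLD change acts through that drinking. It is not a substitute for step 1.
4. **Reconcile the taper passages.** The Zonisamide text, its regimen table and the Table 1 title need to agree on when the taper starts, because the Overview ties the scan date to it. Which of them is right is for the investigators to settle.

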CONN creates subject-specific ROI files and registers them to the subject space. 99 ROIs will be used as the seeds of interest for whole-brain subject-specific ROI-ROI connectivity analyses.

**Power Analysis:** Power analysis for drinks consumed per day during the last three weeks of treatment were determined using data for the placebo and zonisamide groups from our previous study (Knapp et al., 2015). A power value of 0.9 was found for a group size of 40, with alpha=0.05, and with an effect size of 0.74. In our previous study of ZON approximately 20% of subjects dropped out before week 12 of the study. Consequently, we will randomize 50 subjects per group to reach a target of 40 subjects in week 12 of the present study. Based on data reported by Rubio et al. (2009) for errors of commission on the CPT, a measure of impulsivity, a power value of 0.97 would be obtained for an alpha value of 0.05 for a group size of 40. Based on the findings of Myrick et al., (2008) for the difference between the activation of the ventral striatum for placebo and naltrexone groups a power of 0.88 was seen for an effect size of 0.7 for a group size of 40.

**Safety Analysis:** For safety, subjects will be assessed as having had any serious adverse event during the treatment period or not, and additional analyses will be done by separate types of adverse events. Tolerability will be assessed as a subject being able to continue on the study drug for the entire study duration without requiring discontinuation. The safety and tolerability of the study medications will be first assessed using contingency tables and chi-square tests. Fisher's exact test will be employed for rare adverse events. The chi-square analysis will be followed by logistic regression analyses, adjusting for the stratification factor. Time to drug discontinuation for serious adverse events and time to withdrawal from the study for any reason will be assessed using Kaplan-Meier survival curves and compared between study treatments using the log rank test. Poisson regression will be used to evaluate the rate of serious adverse events by arm stratified by the time periods of dosage escalation, dosage maintenance, and dosage taper.

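### Aim 3 states neither who enters the logistic model nor a treatment-arm term; if the arms are pooled, treatment partly confounds the BOLD coefficient

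*Combined protocol and SAP*

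**What the plan says.** All references are to the combined protocol and SAP, Section L.

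- **Data Analysis, item 3 (Aim 3).** The objective is: "Demonstrate that the ZON induced changes in brain activity are predictive of reduced ethanol consumption". The method is one sentence, a logistic regression with "zonisamide-induced decreases in the BOLD response in the ventral striatum and the medial prefrontal cortex as predictors". The binary outcome, assessed over study weeks 10 to 12, is "complete abstinence or reduction to safe drinking levels". No analysis set, arm term, interaction, covariate or mediation step is named. No rule says when one person's decrease counts as caused by zonisamide.
- **Data Analysis, item 2 (Aim 2).** The cue-task activation model is specified "with treatment group as a between group factor and stimulus type and order of stimuli presentation was within subject factors". Its regions "will include the ventral striatum, medial prefrontal cortex, and the anterior cingulate cortex", so both Aim 3 regions are compared by arm there.
- **Other models.** Aim 1 also names treatment group as a factor, Aim 4 names baseline values as covariates, and the Safety Analysis adjusts its logistic regressions for the stratification factor. Only the Aim 3 model is left without stated adjustment among these.
- **Power Analysis.** For drinks per day: "A power value of 0.9 was found for a group size of 40, with alpha=0.05, and with an effect size of 0.74". For ventral striatum activation, from a naltrexone study: "a power of 0.88 was seen for an effect size of 0.7 for a group size of 40". No power or responder rate is given for Aim 3.
- **Overview and Neuropsychological Assessments.** The second scan takes place in study week 12.

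**The concern.** A fall in BOLD response in one person carries no label saying what caused it; only comparison with placebo identifies the part due to the drug. The Aim 3 sentence can be read in two ways, and each has a problem.

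If both arms are pooled, zonisamide participants tend to have larger BOLD decreases and better drinking outcomes, because the plan expects the drug to act on both. That alone produces a correlation between BOLD and drinking across the pooled sample, even if the two are unrelated within each arm. A model without arm reads this as prediction by BOLD.

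If only zonisamide participants enter, treatment cannot confound the coefficient. But the analysis then cannot separate a drug effect from the ordinary tendency of people who drink less to react less to alcohol cues.

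At stake is the trial's mechanistic claim. The Benefits section expects the mechanism results to help identify which patients respond and to guide assessment of related drugs. Aim 3 is the analysis that links brain change to drinking.

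**Working it through.** **1. Reproduce the stated power.** Inputs from the Power Analysis: 40 per group, alpha 0.05 (taken as two-sided), d = 0.74 and d = 0.7. Normal approximation: power = Φ(d·√(n/2) − 1.96).

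- d = 0.74: 0.74 × √20 = 3.309; 3.309 − 1.96 = 1.349; power 0.911 (0.905 with the t distribution), against the stated 0.9.
- d = 0.7: 0.7 × √20 = 3.130; 3.130 − 1.96 = 1.170; power 0.879 (0.871 with t), against 0.88.

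Both agree two-sided; one-sided values (0.952 and 0.931) do not. With "approximately 20% of subjects dropped out before week 12 of the study", 40/(1 − 0.2) = 50 per group, as stated. The inputs are therefore sound as the plan's own planning values.

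**2. Size of the correlation that pooling creates.** Take BOLD decrease and a latent drinking response, each with SD 1 within arm, independent within arm, and shifted by 0.7 and 0.74 in the zonisamide arm. With 1:1 allocation the pooled correlation is

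0.25 × 0.7 × 0.74 / √[(1 + 0.25 × 0.7²)(1 + 0.25 × 0.74²)] = 0.1295/1.130 = 0.115.

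With 80 people and a continuous outcome, Fisher's z gives 0.115 × √77 ≈ 1.01, so the two-sided 5% test rejects in about Φ(1.01 − 1.96) ≈ 17% of trials. A yes/no outcome carries less information, so somewhat less than 17% should be expected.

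**3. Simulation of the logistic model.** Same set-up, 40 per arm, 4,000 trials per row, likelihood-ratio test of one BOLD predictor at 5%. The placebo responder rate p0 is an assumption; the zonisamide rate is Φ(Φ⁻¹(p0) + 0.74). BOLD has no effect within either arm, so every rejection is false.

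| Placebo rate | Zonisamide rate | Pooled, no arm | Pooled, with arm | Zonisamide only |
|---|---|---|---|---|
| 10% | 29.4% | 10.8% | 4.9% | 5.4% |
| 20% | 46.0% | 12.9% | 5.2% | 5.6% |
| 30% | 58.5% | 14.4% | 5.7% | 6.6% |
| 40% | 68.7% | 14.4% | 5.5% | 5.8% |

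Repeat simulations on the same inputs put the overall ranges at about 11% to 16% without arm and 5% to 6% with arm. The median odds ratio per SD of BOLD is about 1.2 without arm and 1.00 with it. With both regions tested jointly the rates are similar: 11.5% to 14.4% without arm, 5.3% to 6.6% with it.

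**4. What the leak depends on** (placebo rate 20%, no arm term, 3,000 trials each). With the drinking shift at 0.74, a BOLD shift of 0, 0.35, 0.7 or 1.0 gives 4.9%, 7.1%, 13.1% and 20.5%. With the BOLD shift at 0.7 but no drug effect on drinking, the rate is 4.9%. Both effects must be present.

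**5. How much of the drug effect is credited to BOLD** (placebo rate 20%). Arm log odds ratio: ln(0.46/0.54) − ln(0.20/0.80) = 1.23. Part carried by BOLD: 0.7 × ln 1.2 = 0.13. Share: 0.13/1.23, about 10%.

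**6. What an arm term does not cure.** Suppose the drug acts only on drinking (0.74) and BOLD merely follows drinking, with 40 per arm and an assumed 20% to 30% placebo response. The between-arm BOLD difference and the arm-adjusted BOLD coefficient are then both significant in about 37% of trials at an assumed correlation of 0.5, and in 64% at 0.7. Passing both tests would not establish that BOLD drives drinking.

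**The case against.** The strongest reply has three parts.

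First, Aim 2 already compares BOLD by arm in both Aim 3 regions. A reader might infer that the missing arm term is what prevents Aim 3 from showing that BOLD changes are drug-induced. That does not follow: an arm term in a model of drinking could not show it either. The randomized comparison in Aim 2 is the right place. This stands, with one reservation: Aim 2 lists group, stimulus type and order but not scan session, so it does not explicitly test a decrease from baseline.

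Second, the sentence may mean zonisamide participants only. An arm term is then impossible and nothing leaks; the rates of 5.4% to 6.6% are close to nominal. This also stands. It makes the unstated analysis set part of the defect, and leaves that reading without a placebo comparison.

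Third, Aim 3 is not among the three hypotheses in the Study Summary (Section G) and has no power statement, and the randomized comparisons in Aims 2 and 4 are untouched. That limits the weight of the point but does not remove it, since the mechanism claim rests on this analysis.

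The simulation also uses inputs that the plan does not supply for zonisamide: no responder rate is given, and 0.7 comes from naltrexone.

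**Conclusion.** The point holds in limited form. Aim 3 leaves open both the analysis set and the treatment term. Under pooling without arm, the false-positive rate for BOLD is about two to three times nominal (11% to 16% against 5%), and adding arm brings it to about 5% to 6%. This assumes effect sizes of 0.7 and 0.74, 40 per arm, normal latent variables with equal SDs, no within-arm link and placebo responder rates of 10% to 40%.

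Two stronger readings are not supported. A reader might infer that any drug effect on drinking would be credited to BOLD; the leak needs effects on both measures and amounts to about a tenth of the arm log odds ratio in the worked case. A reader might also infer that an arm-adjusted coefficient together with a positive Aim 2 result would prove mechanism. It would not: the scan is in week 12 and the outcome covers weeks 10 to 12, so less drinking may have changed BOLD.

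**What to change.** Replace the Aim 3 sentence with a specification that:

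- fits the logistic model on both arms, with BOLD change (week 12 minus baseline) in the named regions, treatment arm and baseline drinking as predictors, and says whether the regions are tested jointly or separately;
- reports the arm-by-BOLD interaction, from an extended model, as an estimate with its confidence interval;
- rests any statement that zonisamide changes BOLD on the Aim 2 between-arm comparison alone, with scan session added to that model so that change from baseline is what is compared;
- describes the arm-adjusted BOLD coefficient as an association, not a demonstrated mechanism.

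No new data are needed. The cost is apparent power. At a 20% placebo rate and assumed within-arm latent correlations of 0.3 and 0.4, power for BOLD is 0.55 and 0.80 with arm, against 0.80 and 0.94 without it (partly confounding) and 0.35 and 0.57 in zonisamide participants only. The interaction will be imprecise: with 80 participants and responder rates of 20% and 46%, about 40 × 0.20 + 40 × 0.46 ≈ 26 responders would be available.

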4. Replicate the finding that ZON will reduce alcohol consumption in AUD subjects. Our working hypothesis is that the drinks consumed per day and percent days drinking will be significantly lower in AUD subjects receiving ZON than in those treated with placebo.

Drinking measures derived from the TLFB data will include the percent days drinking, the number of drinks consumed per day, and the percent days heavy drinking. Heavy drinking will be defined as 4 or more drinks per day for women and 5 or more drinks per day for men.

Alcohol consumption measures will be analyzed using repeated measures mixed models analysis using SAS PROC MIXED (ver 9.3, SAS Institute, Cary, NC) with baseline values for these measures used as covariates. Comparisons will be made for data obtained for the 12 week treatment period for the two conditions.

5. Demonstrate that ZON administration will reduce impulsive and risk taking behaviors. Our working hypothesis is that the ZON will decrease risk taking behavior as assessed using the Rogers Risk Task and the Balloon Analog Risk Task and impulsivity as measured using the Go/NoGo and the Continuous Performance Test (CPT).

Repeated measures mixed models analysis will be used to analyze data obtained for pre-randomization and week 12 data for the Rogers Risk Task, the Balloon Analog Risk Task, the Go/NoGoTask, the CPT, and Go/No Go. Model generated group least square means values for week 12 will be compared using student t-tests.

[name] will provide statistical consultation. He will not have access to identifiable information and will not have any contact with study participants.

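### Aim 3 tests whether brain change predicts reduced drinking with a yes/no outcome alone and no baseline-drinking covariate, which costs power and leaves the test open to confounding

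*Combined protocol and SAP*

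**What the plan says.** Section L, Data Analysis, item 3 states its aim as: "Demonstrate that the ZON induced changes in brain activity are predictive of reduced ethanol consumption". The method is a logistic regression that takes zonisamide-induced decreases in BOLD response "in the ventral striatum and the medial prefrontal cortex as predictors of complete abstinence or reduction to safe drinking levels", the latter "defined as consumption of no more than more than 2 standard drinks per day) during study weeks 10 to 12". The limit is the same for men and women. The item names no covariate and no continuous companion analysis.

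Item 4 of the same section analyses drinks per day and related measures as continuous or percentage outcomes, "with baseline values for these measures used as covariates". That model contains no BOLD predictor. Table 1 schedules the Timeline Follow-Back (TLFB) at screening and through the treatment weeks, so both baseline drinking and drinks per day in weeks 10-12 will be on file.

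The Power Analysis paragraph covers continuous drinks per day in the last three weeks, CPT errors and ventral striatum activation. It gives no power for the item 3 regression.

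**The concern.** The aim is about reduction, but the outcome records whether a participant ends below a fixed level. Inclusion criterion 4 requires an average of at least 14 drinks a week for men or 7 for women, and sets no upper limit. Distance to the limit therefore varies greatly at entry, and starting level will strongly affect who can meet it.

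BOLD change is measured after randomization. The adaptive randomization uses heavy drinking as a factor, but that balances the two arms; it does not balance baseline drinking across participants with larger and smaller BOLD decreases. If baseline drinking is related to BOLD change, the unadjusted model can create an association or hide one.

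Splitting a measured quantity into yes/no also costs power. This is the only planned analysis that links brain change to drinking, so the mechanistic conclusion rests on it.

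**Working it through.** **1. The plan's own figures.** Inputs from the Power Analysis paragraph: "A power value of 0.9 was found for a group size of 40, with alpha=0.05, and with an effect size of 0.74". Sidedness is not stated; two-sided is assumed.
- Drinks per day: 0.74 × √(40/2) = 3.309, and Φ(3.309 − 1.960) = 0.911 (0.905 by the t-test). Stated: 0.90.
- Ventral striatum, effect size 0.7: 0.879 (0.871 by the t-test). Stated: 0.88.
- Dropout: 40 / (1 − 0.20) = 50 per group. Stated: 50.

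These reproduce; one-sided calculations (0.95 and 0.93) do not. None of them concerns item 3.

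**2. Who can meet the outcome**, reading the limit as a mean over weeks 10-12:
- A man entering at 15 drinks a week (15/7 = 2.14 a day) succeeds at 14 a week, a cut of 1/15 = 6.7%.
- A man who halves from 70 to 35 a week ends at 5 a day and fails.
- Exclusion criterion 12 uses a safe level of 2 a day for men and 1 a day for women. A woman averaging above 1 and up to 2 a day can therefore enter already meeting the item 3 outcome.

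**3. Information lost by splitting.** For a normal outcome split at success rate p, the efficiency relative to the continuous analysis is φ(z_p)² / [p(1 − p)]. At p = 0.50 this is 0.3989² / 0.25 = 0.637.

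| Success rate | Efficiency | Loss | Effective n out of 80 |
|---|---|---|---|
| 50% | 0.637 | 36% | 51 |
| 40% | 0.622 | 38% | 50 |
| 30% | 0.576 | 42% | 46 |
| 20% | 0.490 | 51% | 39 |
| 10% | 0.342 | 66% | 27 |

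**4. Power, by simulation.** Assumed: y = −0.30x + 0.5b + e with unit variances, where x is the BOLD decrease, b baseline drinking (independent of x here) and y drinking in weeks 10-12. Success means y below the quantile for a success rate between 15% and 50%.

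| Model | n = 80 | n = 40 |
|---|---|---|
| Logistic, no baseline (as planned) | 0.43-0.59 | 0.27-0.34 |
| Logistic with baseline | 0.50-0.68 | 0.32-0.40 |
| Linear with baseline | 0.89 | 0.59 |

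The 80 is the week-12 target of 40 per group. The 40 applies if the reference to zonisamide-induced decreases means the zonisamide arm alone.

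Zeros narrow the gap in some settings. At n = 80, with 50% successes of whom 30 percentage points are abstinent, power was 0.74 (linear) against 0.61 (logistic) unadjusted, and 0.85 against 0.69 adjusted. That is a loss of about 26% to 33%. At 25% successes with 15% abstinent it was 0.80 against 0.52 unadjusted, a gap as wide as under a normal outcome.

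**5. False positives with no true BOLD effect.** Same model with slope 0, n = 80 and 30% successes, but with x and b correlated:

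| Correlation of baseline drinking and BOLD change | Unadjusted logistic | With baseline |
|---|---|---|
| 0 | about 5% | about 5-8% |
| 0.2 | about 12% | about 5-8% |
| 0.3 | about 17% | about 5-8% |
| 0.5 | about 40% | about 5-8% |

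**The case against.** A responder outcome has a purpose here. Section N says that the findings may help to separate people who respond to zonisamide from those who do not, and a yes/no outcome answers that directly. Item 3 is not among the three hypotheses in the Section G summary, and item 4 already analyses drinking on its natural scale. Making the logistic model secondary is therefore partly a matter of preference. The argument does not explain the missing baseline term, and item 4 cannot stand in for item 3 because it has no BOLD predictor.

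Three limits on the working also stand. The drinking limit could mean a ceiling on every day instead of a period mean, and then the examples in step 2 need not hold. The 80 is a retention target, not a count of usable scan pairs. The simulated outcome is normal, while real drinking data will be skewed with zeros.

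A reader might infer that about half the information is lost. That holds only for success rates near 20% or 80%, and the documents give no rate. A reader might also infer that the analysis is confounded as planned. The documents neither state nor exclude a correlation between baseline drinking and BOLD change, and at zero correlation the false-positive rate is not inflated. The predictor is itself a decrease in BOLD response, with scans before treatment and in week 12, so what is left out is baseline drinking, not baseline brain activity.

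**Conclusion.** The concern holds as a gap in the item 3 model. An aim about reduction is tested only against a fixed level, starting level is left out, and this is inconsistent with item 4. Confounding is a risk whose size depends on a correlation that nobody has stated; adding baseline drinking removes nearly all of it under the assumptions used. The information lost by splitting is a range, roughly 36% to 66%, and a guide only.

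The ordering of the models is firmer than the power figures. At the assumed slope of 0.30 and 80 participants, the planned analysis has about a 43-59% chance of detecting the association, against about 89% for the baseline-adjusted linear model. All figures are lower if one arm is used. The change should be made, but this is an improvement to one mechanistic aim and does not touch the drinking comparison between arms.

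**What to change.** 1. Add baseline drinks per day from the TLFB as a covariate in the item 3 logistic model.
2. Prespecify a regression of log(1 + mean drinks per day, weeks 10-12) on BOLD change, with baseline log drinks per day as a covariate. Preferably make this the main test of reduced consumption, and keep the adjusted logistic model as the responder summary.
3. State whether the limit in item 3 is a period mean or a daily ceiling, and whether one arm or both enter the model.
4. Reconcile the safe-drinking definitions in exclusion criterion 12 and in item 3.

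The cost is plan wording and one extra model, with no new data. The downside is that the main result becomes a slope and not an odds ratio, which is harder to put in clinical terms; the retained logistic model covers that.
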